#### 7.2.3.4 Time to death (from all causes)

If a patient dies on or prior to Day 379, the date of death will be obtained from the ‘Disposition Study Completion’ eCRF. The time to death in weeks will be derived as (date of death – date of randomization +1)/7 .

If a patient does not die on or prior to Day 379, the same censoring rules will apply as in Section 7.2.3.3.

The superiority of GB0139 3mg compared to Placebo for time to death from all causes from date of randomization will be tested, regardless of the number of events.

	Plus-Project Statistical Analysis Plan	
	Protocol Number: GALACTIC-1	Version: 1

The null hypothesis is:

$H_0$ : There is no difference in time to death for all causes between GB0139 3mg and Plc.

The alternative hypothesis is:

$H_a$ : There is a difference in time to death for all causes between GB0139 3mg and Plc.

The same model will be used as described in Section 7.2.3.3.

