14.1 Statistical and Analytical Plans

A blinded data review will be conducted prior to database lock. This review will assess the accuracy and completeness of the study database, subject evaluability, and appropriateness of the planned statistical methods.

A statistical analysis plan (SAP) will be prepared and finalized prior to database lock. This document will provide further details regarding the definition of analysis variables and analysis methodology to address all study objectives.

For descriptive statistics categorical data will be presented as frequencies and percentages. Percentages will be based on the number of subjects with non-missing values for the corresponding categorical variable. Continuous data will be presented as number of subjects with non-missing values, mean standard deviation, median, minimum and maximum, as well as the 25th and 75th percentile.

All statistical tests as well as the confidence intervals will be two-sided. The study-wise type I error probability for the confirmatory analyses is set to 10%. 90% confidence intervals are to be calculated, if feasible.

Covariates for the primary analyses will be pre-specified. For secondary analyses these are anticipated to be broadly similar to primary analysis but will be fully specified in the Statistical Analysis Plan (SAP).

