14.4.2.1 Key Secondary Endpoints

The key secondary analysis will be based on data from SoC2 only. Data will be summarized graphically and using summary statistics. The multiplicity procedure used for the key secondary endpoints will be detailed in the SAP.

Comparisons between treatment groups regarding the binary endpoint variable based on an absolute decline from baseline in FVC % predicted of $\leq 10\%$ will be performed using a logistic regression model. Treatment and baseline FVC (mL) will be included in the model along with any other covariates included in the analysis of the primary endpoint. The likelihood-ratio test will be used to test for differences between treatments. Odds ratios together with 90% confidence intervals will be used to quantify the effect of treatment, comparing GB0139 3 mg to placebo as the reference.

The change from baseline in the SGRQ total score at Week 52 will be analysed using a mixed model repeated measures with covariates treatment, baseline total score along with any other covariates included in the analysis of the primary endpoint.

The time to first hospitalization (respiratory related, including acute exacerbation of IPF) will be analysed using a Cox proportional hazards model with covariates treatment, baseline FVC (mL) along with any other covariates included in the analysis of the primary endpoint. The equality of the hazard rates between the GB0139 3 mg and placebo group will be tested by the Wald test for the treatment effect. The model will include treatment as covariates. Breslow's method for handling ties will be used. Kaplan-Meier plots by treatment group will also be presented.

Time to death from all causes (plus death from respiratory-related causes if numbers allow) will be analysed using a Cox proportional hazards model. The equality of the hazard rates between the GB0139 3 mg group and placebo will be tested by the Wald test for the treatment effect. The model will include treatment, baseline FVC (mL) as covariates along with any other covariates included in the analysis of the primary endpoint. Breslow's method for handling ties will be used. Kaplan-Meier plots by treatment group will also be presented. If the proportion of deaths is less than 5%, then only frequencies of deaths by treatment group will be provided for the key secondary endpoint of time to death and no statistical analysis will be performed.

14.4.2.2 *Other Secondary Endpoints*

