A Cox proportional hazards model will be fitted with treatment and baseline FVC (mL) included in the model. The Wald test will be used to test for differences between treatments. Hazard ratios together with 90% and 95% confidence intervals will be used to quantify the effect of treatment, comparing GB0139 3mg to Placebo as the reference. Breslow’s method for handling ties will be used.

The analysis will be repeated by subgroup (separately for each subgroup factor of interest) by adding a fixed effect for the subgroup factor and adding a treatment by subgroup interaction term. The hazard ratio between treatments will be assessed within each level of the subgroup.

If there are fewer than 15 events (respiratory related, including acute exacerbation of IPF) then a formal statistical analysis will not be performed, and only frequencies of hospitalizations by treatment group will be provided. If an overall analysis is performed, then the subgroup analyses will automatically be performed, regardless of the number of events in the subgroup levels.

Kaplan-Meier plots by treatment group will also be presented.

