#### 7.2.4.9 Time to respiratory-related death

Respiratory related causes will be defined as in Section 7.2.3.3. The time to death due to respiratory related causes, in weeks, will be derived as (date of respiratory-related death – date of randomization +1)/7.

If a patient does not die due to respiratory related causes on or prior to Day 379, the same censoring rules will apply as in Section 7.2.3.3.

Cox proportional hazards modelling, as detailed in Section 7.2.3.3, will be performed.

	Plus-Project Statistical Analysis Plan	
	Protocol Number: GALACTIC-1	Version: 1

7.2.4.10 Change in FVC expressed in mL over 52 weeks for subjects who have never been treated with pirfenidone or nintedanib

The same data source and analyses (random coefficients regression model) as detailed in Section 7.2.1 will be used. Statistical analysis will be performed for the Primary Population and descriptive analyses only for the SoC2 / Monotherapy Population.

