## 9. CHANGES TO STATISTICAL ANALYSIS FROM PROTOCOL

The following clarifications have been made compared to the statistical analysis documented in the protocol at the time of writing (Version 7.0, 28 January 2022):

The protocol stated that two separate sensitivity analyses would be carried out for the primary estimand, and a tipping point analysis. The tipping point analysis described was looking for the tipping point between two sensitivity analyses, rather than relating to the primary analysis, and so was considered not to be informative and was removed. The second sensitivity analysis was also removed.

The protocol stated that for the endpoint of time to death, if fewer than 5% of subjects experienced the event during the study then only frequencies per treatment group would be displayed and no formal statistical analysis would be performed. The threshold for deaths has been removed and time to death will be analyzed regardless of the number of events.

In the logistic regression analyses the Wald test will be used rather than a likelihood ratio test.

The protocol defined a subgroup of subjects recruited prior to Protocol version 6.0 vs subjects recruited post v6.0, which is also removed.

[figure not shown]

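### Time to death is tested at any death count with a Cox Wald test, which gives p near 1 and no usable hazard ratio if one arm has no deaths

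*SAP*

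**What the plan says.** Time to all-cause death is a key secondary endpoint. SAP 7.2.3.4 states that superiority "from date of randomization will be tested, regardless of the number of events", and adds: "The same model will be used as described in Section 7.2.3.3". In SAP 7.2.3.3 that model is a Cox regression on treatment and baseline FVC with Breslow ties, and "The Wald test will be used to test for differences between treatments". Hazard ratios are reported with 90% and 95% confidence intervals.

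The protocol (14.4.2.1) also specified the Wald test for death, but behind a gate: "If the proportion of deaths is less than 5%, then only frequencies of deaths by treatment group will be provided". SAP section 9 removes the gate openly: "The threshold for deaths has been removed and time to death will be analyzed regardless of the number of events".

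For respiratory hospitalization SAP 7.2.3.3 keeps a floor: "If there are fewer than 15 events (respiratory related, including acute exacerbation of IPF) then a formal statistical analysis will not be performed". SAP 7.2.4.7 and 7.2.4.8 restate a 15-event floor for IPF-related and all-cause hospitalization. SAP 7.2.4.9, on respiratory-related death, says only: "Cox proportional hazards modelling, as detailed in Section 7.2.3.3, will be performed". Neither document gives a fallback for an arm with no deaths.

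**The concern.** A Wald test divides the estimated log hazard ratio by its standard error. When one arm has no events there is no finite estimate: the partial likelihood keeps rising as the coefficient grows, while the information about the coefficient shrinks to zero. The standard error therefore outgrows the estimate, the test statistic goes to zero and p goes to 1. The usual Wald confidence interval then covers everything and says nothing.

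This happens only when deaths are few or one-sided. The SAP chose to test in that setting when it removed the 5% gate, and left the test statistic unchanged. The planned result for a key secondary endpoint could then be a non-estimable hazard ratio with p near 1, printed beside death counts that clearly differ. Respiratory-related deaths are a subset of all deaths, so that endpoint is more exposed.

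**Working it through.** **The plan's own figures.** The documents give no expected number of deaths and no power for this endpoint. The only power figure, 75%, is for FVC. It reproduces with 47 placebo and 94 active subjects: 240 × √(1/47 + 1/94) = 42.9; 100/42.9 − 1.645 = 0.687; Φ(0.687) = 75.4%. It does not bear on death, but it supplies the 47/94 split used below.

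**Why the tests differ, by hand.** Take 0/47 versus *d*/94 deaths and ignore the slow shrinkage of the risk sets. Each death contributes 1/141 to the partial likelihood under no effect, and up to 1/94 as the coefficient grows.
- Likelihood ratio: 2 × *d* × ln(141/94) = 0.811*d*. For *d* = 10 this is 8.11, p = 0.004.
- Score (log-rank): observed minus expected is *d*/3 and the variance is 2*d*/9, giving *d*/2. For *d* = 10 this is 5.0, p = 0.025.
- Wald: no finite estimate.

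**Refit of the planned model.** Cox regression with Breslow ties, treatment and a baseline covariate, follow-up to Day 379 (SAP 5.2), 100 simulated data sets per row, median p-values. The score test is unadjusted.

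| Deaths, placebo v active | Wald | Likelihood ratio | Score |
|---|---|---|---|
| 0/47 v 5/94 | 0.999 | 0.042 | 0.110 |
| 0/47 v 10/94 | 0.999 | 0.004 | 0.022 |
| 5/47 v 0/94 | 0.999 | 0.0008 | 0.0012 |
| 7/47 v 0/94 | 0.999 | 0.0001 | 0.0001 |
| 1/47 v 10/94 | 0.116 | 0.051 | 0.079 |
| 5/47 v 1/94 | 0.032 | 0.010 | 0.008 |

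In the 0/47 v 10/94 row the fitted log hazard ratio is 20.7 with a standard error of about 13,600, so z = 0.0015. In the 1/47 v 10/94 row nothing diverges, but the Wald test falls on the other side of the two-sided 10% level from the other two. Protocol 14.1 sets that level: "The study-wise type I error probability for the confirmatory analyses is set to 10" percent.

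**How often exactly one arm is empty.** The mortality rates *q* are assumptions, taken as equal in both arms. The probability is (1−*q*)^a + (1−*q*)^b − 2(1−*q*)^(a+b). At *q* = 3% with a 47/94 split: 0.239 + 0.057 − 2 × 0.014 = 0.27.

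| Mortality | 47/94 | 70/71 |
|---|---|---|
| 3% | 27% | 21% |
| 5% | 10% | 5% |
| 10% | 0.7% | 0.1% |

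The true split lies between these columns. The Primary Population (SAP 1.3) includes SoC2 subjects from the original design, who were randomized equally to 3 mg and placebo (SAP 3.2).

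**The other end of the range.** Protocol 4.1 quotes a median survival of 2 to 3 years from diagnosis. If that applied exponentially, mortality by Day 379 would be 1 − 0.5^(1.038/3) = 21% to 1 − 0.5^(1.038/2) = 30%. An empty placebo arm would then have probability at most 0.787^47, about 1 in 80,000.

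**If the drug worked very well.** With an assumed 5% placebo mortality and hazard ratio 0.2, the 94-subject active arm has no deaths with probability 0.95^(94 × 0.2) = 38%.

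**The case against.** **Probability.** The chance of an empty arm is not the chance that it matters. With 0/47, the likelihood-ratio test reaches the 10% level only from 4 active deaths (0.811 × 4 = 3.24, p = 0.07). At equal mortality, no placebo deaths together with at least 4 active deaths has probability about 7% at 3% mortality and 6% at 5%. Those would also be false positives. This stands, and so does the point that the background survival figure would make an empty arm very unlikely. That figure counts from diagnosis, however, whereas the trial enrolls people up to five years after diagnosis and above lung-function minimums. It does not settle the trial's mortality. The 5% gate shows that few deaths were thought possible, but it is not a forecast.

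**Safety.** A reader might infer that a mortality signal could be missed. The documents do not support that. Kaplan-Meier plots are planned (SAP 7.2.3.3). SAP 7.3.2 provides counts of all deaths, risk differences for adverse events leading to death and a listing of deaths. The DSMB reviews death cases (Protocol 12.1), and Protocol 14.5.2 plans no hypothesis tests for safety.

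**Consequences.** SAP 7.1.3 makes no multiplicity adjustment, so no other test waits on this one, and SAP section 5 treats efficacy p-values as exploratory. A statistician would recognize the failed fit. This limits the damage, but SAP 7.2.3.4 still states a formal null hypothesis and names the test.

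**Inconsistency.** A reader might take the 15-event floor for hospitalization, and none for death, as a contradiction. It is not. The floor is worded for hospitalizations, SAP 7.2.3.4 expressly overrides any such limit for all-cause death, and the change from the protocol is disclosed. Dropping the gate is defensible; the gap is in the test that remains.

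**Conclusion.** The point holds as a defect in the planned test statistic for all-cause and respiratory-related death. Given an empty arm, Wald p near 1 is a mathematical certainty and needs no assumption about mortality. With a single death in one arm, the choice of test can already decide the result at 10% (1/47 versus 10/94: 0.12 Wald, 0.05 likelihood ratio).

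How likely an empty arm is cannot be fixed from the documents. Under the assumed equal mortality rates and a 47/94 split it ranges from 27% at 3% mortality to under 1% at 10%, and to practically zero at the background survival figure. The subgroup Cox models of SAP 7.2.3.3, which run whatever the event count in each level, meet empty cells more easily; they report hazard ratios without p-values.

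What is at stake is the formal test of a key secondary endpoint and its hazard ratio. Safety monitoring is not affected.

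**What to change.** Keep testing at any death count. In SAP 7.2.3.4 and 7.2.4.9, replace the Wald test with one named test: the likelihood-ratio test for treatment from the planned Cox model with baseline FVC. Report the hazard ratio with profile-likelihood 90% and 95% confidence intervals. If an arm has no deaths, report a Firth-penalised hazard ratio with profile-likelihood intervals, and say that the p-value still comes from the likelihood-ratio test. Show deaths by arm beside the result.

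Only one test should be named. For 0/47 versus 4/94 or 5/94, the hand formulas give 0.07 and 0.04 for the likelihood ratio against 0.16 and 0.11 for the score test, on opposite sides of 10%. Leaving the choice open would add an analyst's decision exactly where data are sparse. The likelihood-ratio test also keeps the planned baseline adjustment, which a log-rank test drops.

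The cost is a sentence or two in the SAP, listed in section 9 as a further departure from the protocol, using standard software options. With plentiful events the tests nearly agree. The one downside is that the likelihood-ratio test is somewhat less conservative than the score test when events are very few, which is why the counts should stand next to it.

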#### **7.2.4 Other Secondary Endpoint Analysis**

Unless otherwise stated, all other secondary endpoints will be statistically analyzed only for the Primary Population. For the SoC1 / Combination and SoC2 / Monotherapy Populations, only descriptive summaries will be provided. All analyses will use the mITT set, unless otherwise specified.

No subgroup analyses will be performed for these endpoints.

##### **7.2.4.1 Proportion of subjects with an absolute decline from baseline in % Predicted FVC of $\leq 5\%$ at Week 52**

The same data source and analyses (logistic regression) as detailed in Section 7.2.3.1 will be used.

##### **7.2.4.2 Change from baseline in 6-minute walk test (6MWT) distance over 52 weeks**

Data from an external vendor with the 6MWT results will be used. To compare the change from baseline in the distance covered in the 6MWT at Week 52, an Analysis of Covariance (ANCOVA) will be fitted with treatment and baseline 6MWT distance included in the model. The least squares means per treatment and difference in least square means between treatments and 90% and 95% CI will be presented.

Data collected at early withdrawal visit will be summarized descriptively only.

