2.2 Study Time and Events Schedule

Table 1: Study Time & Events Schedule

Visit	1	2	3	4	5	6	7	8	Withdrawal ⁹	Follow up ⁷
	Screening ¹	Baseline	Treatment							
Weeks of treatment		0	4	8	12	26	40	52	-	
Day Time window	6 weeks	0	29 ±3	57 ±3	85 ±3	183 ±7	281 ±7	365 ±7		7 days after final study visit (+7 days)
Informed consent	X									
HRCT sent to central review	X									
Demographics (including height, weight)	X									
Medical history	X									
Randomization		X								
In- /exclusion criteria	X	X								
Physical examination, vital signs	X	X	X	X	X	X	X	X	X	
HRQoL (SGRQ, SF-36)		X			X	X		X		
Dyspnoea index (UCSD-SOBQ)		X			X	X		X		
12-lead ECG	X	X	X	X	X	X		X	X	
Laboratory test (chemistry, haematology) ²	X	X	X	X	X	X	X	X	X	
Urinalysis	X		X	X	X	X	X	X	X	
Pregnancy test ^{3, 4}	X	X	X	X	X	X	X	X	X	
Biomarker sample		X	X		X	X		X		
Genetics sample ⁵		X								
Spirometry (FVC, FEV1)	X	X	X	X	X	X	X	X	X	
SpO ₂		X						X		
DLCO	X							X	X	
6MWT		X						X	X	
Administer 1st study medication (at clinic) & inhaler training ⁶		X								
Dispense trial drug		X	X	X	X	X	X			
Compliance / drug accountability ⁷			X	X	X	X	X	X	X	
Adverse events & conc. meds ⁸	X	X	X	X	X	X	X	X	X	X

Notes:

1. HRCT confirmation by central reading must be obtained as soon as possible following screening visit 1 and prior to visit 2
2. See [Table 2](#) and [Table 3](#) Section 10.4.9

3. In women of childbearing potential only: serum b-HCG will be required at visit 1 only, followed by urinary testing at subsequent visits.
4. This is optional and separate consent must be obtained. The sample can be taken at other study visits.
5. Subjects should be observed for 1 hour after the first dose to monitor for any acute adverse effects of study drug administration (e.g., bronchospasm – see Section 8.1)
6. Includes checking the subject's use of the DPI device (Plastiape monodose inhaler)
7. The follow-up will be performed via a phone call.
8. Events occurring prior to randomization and administration of drug are considered as pre-treatment (as defined in Section 11.1.1). Adverse events are also collected for up to the phone follow up.
9. FVC, DLCO and 6MWT will be performed as part of the withdrawal assessments.

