14.4.2 Analysis of Secondary Endpoints

For all secondary endpoints, an intent-to-treat principle will be used.

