### 7.1.2 Methods for Handling Missing Values

In general, missing data will not be imputed. Exceptions are detailed in the subsequent sections.

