##### **7.2.4.3 Change from baseline in diffusion capacity of the lung for carbon monoxide (DLCO), corrected for HB, at 52 weeks**

Data from an external vendor with the DLCO result (mmol/min/kPa) will be used. The same analyses (ANCOVA) as detailed in Section 7.2.4.2 will be used but using the baseline DLCO rather than baseline 6MWT in the ANCOVA model.

Data collected at early withdrawal visit will be summarized descriptively only.

	Plus-Project Statistical Analysis Plan	
	Protocol Number: GALACTIC-1	Version: 1

7.2.4.4 Change from baseline at week 52 in dyspnea assessment by University of California San Diego - Shortness of Breath Questionnaire (UCSD - SOBQ)

Data from an external vendor with the UCSD – SOBQ scores will be used. The UCSD – SOBQ comprises of 24 items scored 0-5 where (0 = "not at all" to 5 = "maximal or unable to do because of breathlessness"). The item scores will be summed (treating any missing as 5) to derive a total score between 0 and 120. The UCSD – SOBQ items are provided in Section 11.7. The same MMRM analysis as detailed in Section 7.2.3.2 will be used for the change from baseline at week 52 in UCSD – SOBQ Total Score, using the baseline UCSD – SOBQ Total Score rather than the baseline SGRQ Total Score.

7.2.4.5 Change from baseline at Week 52 for HRQoL as assessed by Short Form Survey (SF-36)

Data from an external vendor with the SF-36 scores will be used. The change from baseline in SF-36 total score will be analyzed using an MMRM the same as detailed in Section 7.2.3.2 using the corresponding baseline SF-36 total score rather than the baseline SGRQ total score.

In addition, the actual and change from baseline in individual component scores as follows will be summarized by treatment group and visit:

- Physical component scale (PCS) and mental component scale (MCS).
- Physical functioning (PF), role physical (RF), bodily pain (BP), general health (GH), vitality (VT), social functioning (SF), role emotional (RE) and mental health (MH).

The details of scoring are provided in Section 11.8.

7.2.4.6 Percentage of subjects with Adverse Events (AE) or Serious Adverse Events (SAE) over 52 weeks

Only TEAEs with a start date prior to Day 379 will be considered for inclusion in the analysis. Summaries of the percentage of subjects with AE or SAEs will be presented for each population by SOC and PT. No formal analyses will be performed.

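### 6MWT and DLCO are compared only among survivors with a Week 52 assessment: withdrawal values stay outside the test and deaths have no rule

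*SAP*

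**What the plan says.** **Model.** SAP 7.2.4.2: "To compare the change from baseline in the distance covered in the 6MWT at Week 52, an Analysis of Covariance (ANCOVA) will be fitted". The model terms are the randomised arm and the starting distance. SAP 7.2.4.3 carries this over to DLCO: "The same analyses (ANCOVA) as detailed in Section 7.2.4.2 will be used but using the baseline DLCO rather than baseline 6MWT".

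**Withdrawal data.** Both sections end with the same sentence: "Data collected at early withdrawal visit will be summarized descriptively only". Yet the protocol plans these measurements; note 9 to Table 1 (Protocol 2.2) says "FVC, DLCO and 6MWT will be performed as part of the withdrawal assessments".

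**Missing data and analysis set.** SAP 7.1.2: "In general, missing data will not be imputed". Exceptions are left to later sections, and none covers 6MWT or DLCO. SAP 7.2.4: "All analyses will use the mITT set, unless otherwise specified". Protocol 14.4.2: "For all secondary endpoints, an intent-to-treat principle will be used".

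**Visit mapping.** SAP 5.2 assigns the non-missing result closest to the scheduled day within a window. The Week 52 window opens on Day 324. Results after Day 453 are left out of the efficacy analyses.

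**The concern.** The protocol schedule has 6MWT and DLCO before treatment, at Week 52 and at withdrawal, and at no other time. An early leaver therefore has no intermediate value for a model to use, and the one follow-up value that may exist is kept out of the test. A subject who dies before Week 52 is also absent.

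The documents give reasons to think that those who are missing may be sicker. Protocol 10.6 lists death and lung transplant among the reasons for leaving the study. Protocol Appendix 3 links lower DLCO and shorter walk distance to more acute exacerbations. Protocol 6.4 says exacerbations carry a substantial risk of hospitalization and death. Adjusting for baseline removes only the part of this that baseline predicts, not worsening during the trial.

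At stake is how a nominal difference in exercise capacity or gas transfer is read. If one arm loses more of its sicker patients, its remaining patients look better for that reason alone.

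**Working it through.** **1. The plan's own figure.** The only power statement for the current design concerns FVC: 141 subjects at 2:1 (47 placebo, 94 active), difference 100 mL, SD 240 mL, two-sided 10%. The standard error is 240 × √(1/47 + 1/94) = 42.9 mL and 100/42.9 = 2.33. Power is Φ(2.33 − 1.645) = 0.754, so the stated 75% is reproduced. The documents give no SD, effect size or expected missingness for 6MWT or DLCO, so there is no figure to check for these endpoints.

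**2. Who enters each comparison.**

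| Endpoint | Follow-up values in the model | Rule for death or departure |
|---|---|---|
| FVC slope (SAP 7.2.2) | all visits | death takes the lowest value recorded in the trial |
| FVC % predicted responder (7.2.3.1) | Week 52 | loss to follow-up counts as decline above 10% |
| SGRQ, UCSD-SOBQ, SF-36 (7.2.3.2, 7.2.4.4, 7.2.4.5) | Weeks 12, 26, 52 in an MMRM | none for death; earlier visits inform the model |
| 6MWT, DLCO (7.2.4.2, 7.2.4.3) | Week 52 only | none |

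Only the last row combines a single follow-up time with no rule at all. Subjects who stop study drug may stay in the study (Protocol 10.5), so they can still supply a Week 52 value.

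**3. Size of the risk.** All inputs here are assumptions. Suppose there is no true effect, a share q of an arm lacks a Week 52 value, and missingness follows a latent normal variable. Let ρ be the correlation between staying in the study and a better residual outcome. The mean among those observed is then too high by ρ × φ(z_q)/(1 − q) SD, where z_q is the normal quantile of q.

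- q = 15%: 0.2332/0.85 = 0.2743
- q = 25%: 0.3178/0.75 = 0.4237
- gap: 0.1494
- shift: 0.045, 0.075 and 0.105 SD for ρ = 0.3, 0.5 and 0.7

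For 10% versus 30%, the gap is 0.3477/0.7 − 0.1755/0.9 = 0.302, and the shift is 0.09 to 0.21 SD. With equal q in both arms it is zero. The shift always favours the arm with more missing values.

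**4. The same risk in metres, for 6MWT.** Assume leavers lose 40, 60 or 80 m more than those assessed, a 10-point gap in leaver share, and no difference among those assessed. The difference left out is 40, 60 or 80 × 0.10 = 4, 6 or 8 m.

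**5. Would a longitudinal model recover it?** One option is to fit change on baseline, time and treatment-by-time, using every follow-up value, and read off Week 52. I simulated this with 47 versus 94 subjects, leavers at 20% versus 30% or 15% versus 25%, half of them attending the withdrawal visit, and an assumed SD of 70 m. It recovered only about 0.5 to 1.6 m of the 4 to 8 m. Each leaver has one follow-up value, at the time of leaving, so the Week 52 estimate is driven by those seen at Week 52.

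**The case against.** The strongest case against runs as follows.

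- **Status.** These are other secondary endpoints. Protocol 14.4.2.2 calls them exploratory, with nominal p-values. This stands, and it limits the importance of the point.
- **Death is analysed elsewhere.** It enters the primary FVC analysis and has its own all-cause and respiratory-related endpoints. SGRQ, UCSD-SOBQ and SF-36 have no death rule either. This also stands: the lack of a death rule is not peculiar to 6MWT and DLCO. What is peculiar is that nothing else compensates.
- **The ANCOVA may be unbiased.** If missingness depends only on arm and baseline, an observed-case ANCOVA adjusted for baseline is valid. Correct, but the plan contains no check of that assumption for these endpoints.
- **The protocol leaves the detail to the SAP.** It prescribes no model for 6MWT or DLCO, so the SAP does not contradict a named method. The tension is with the stated intent-to-treat principle, and SAP section 9 does not list it as a change.

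A reader might infer that the withdrawal values are thrown away, or that only treatment completers are compared. Neither follows. The values are summarised descriptively, and subjects off study drug can attend Week 52.

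**Conclusion.** The point holds as a gap in the plan. The 6MWT and DLCO tests are restricted to survivors with a Week 52 assessment, withdrawal values are excluded from the treatment comparison, and deaths have no rule.

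A reader might go further and conclude that the comparison is biased, or that a real difference will be hidden or reversed. The documents do not support that. They give no dropout rates by arm and no variability for either endpoint, so neither size nor direction can be known. The 0.045 to 0.105 SD shift depends on 15% versus 25% missingness and correlations of 0.3 to 0.7. The 4 to 8 m depends on an assumed extra decline and an assumed gap in leaver share. Equal missingness gives no shift in the first model, and equal leaver shares give none in the second.

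The primary conclusion does not depend on these endpoints. This is an inexpensive improvement, best settled before unblinding.

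**What to change.** **Keep** the Week 52 ANCOVA for both endpoints.

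**Add** to SAP 7.2.4.2 and 7.2.4.3 a supportive rank ANCOVA of change over the mITT set, adjusted for baseline:

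- Deaths before Week 52 are ranked worst.
- Subjects who leave alive are ranked by their change at the withdrawal visit, and all others by their Week 52 change.
- Each subject contributes one value, and nothing after Day 453 is used. This matters because Protocol 10.3.3.1 sends some original-design subjects who were already past Week 52 to a withdrawal visit, so they may have both values.
- State what happens to subjects alive with neither value, and report their number by arm.

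**Resolve** the mapping conflict. Under SAP 5.2 a withdrawal result on or after Day 324 could be taken as Week 52, while 7.2.4.2 and 7.2.4.3 keep withdrawal data descriptive. Say which rule prevails.

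**Do not** rely on a treatment-by-time model for this purpose, for the reason shown in step 5 of the working.

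**Cost.** SAP wording and one extra analysis per endpoint, with no new data. A rank-scale effect is harder to interpret than metres or DLCO units. Withdrawal values are taken before Week 52 and may understate later decline, so the analysis reduces the survivor problem without removing it.
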